Another potential reason for intervention is hypotony. Intervention should only be considered if the hypotony has caused or is likely to cause sequelae such as a flat chamber or retinal detachment. No intervention is indicated when the vision is unchanged from screening, there is no persistent choroidal detachment, the anterior chamber is not flat with lens corneal touch, or the patient is asymptomatic. No intervention should be undertaken for hypotony which is not causing, or threatening to cause, a reduction in vision.

Secondary IOP-Lowering Interventions to Control IOP

If the subject requires another glaucoma procedure to control their IOP, the subject should continue to be followed according to standard of care until the adverse event resolves or 1-month post-re-intervention, whichever is longer. Following this, the subject should be withdrawn from the study.

Subjects who have had a secondary IOP-lowering intervention will be considered treatment failures for the purpose of the endpoint analyses. For the primary effectiveness endpoint of the study, the corresponding baseline unmedicated DIOP will be used to impute the 12-month unmedicated DIOP. These subjects will be included in the Safety Endpoint analyses through their withdrawal from the study.

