10 STATISTICAL CONSIDERATIONS

10.1 SAMPLE SIZE CALCULATION

The sample size calculation is based on the primary effectiveness endpoint, mean change in unmedicated DIOP from baseline at the 12-month postoperative examination. The study goal is to determine, in reducing the IOP in eyes with OAG undergoing cataract extraction, either OMNI (ab-interno transluminal viscoelastic delivery AND trabeculotomy) is superior [REDACTED], or OMNI (ab-interno transluminal viscoelastic delivery alone) is not inferior to the [REDACTED] in lowering the IOP with a non-inferiority margin of 1.5 mmHg. Due to the multiplicity, the significance level is adjusted to a two-sided significance level of 0.025 for each of the two hypotheses. The statistical hypotheses for the primary effectiveness endpoint are as follows:

Hypothesis I:

$H_0: \mu_{02} = \mu_i$ versus $H_a: \mu_{02} < \mu_i$, where μ_{02} and μ_i are the mean change in unmedicated DIOP from baseline at the 12-month postoperative examination for the OMNI (ab-interno transluminal viscoelastic delivery AND trabeculotomy) and [REDACTED] groups, respectively. A negative mean change represents a mean reduction. The alternative hypothesis ($H_a: \mu_{02} < \mu_i$) is to prove that the mean change in unmedicated DIOP of the OMNI (ab-interno transluminal viscoelastic delivery AND trabeculotomy) group is lower than that of the iStent inject group. In other words, the OMNI (ab-interno transluminal viscoelastic delivery AND trabeculotomy) is superior to the [REDACTED] group in lowering the IOP.

Hypothesis II:

$H_0: \mu_{01} - \mu_i \leq -1.5 \text{ mmHg}$ versus $H_a: \mu_{01} - \mu_i > -1.5 \text{ mmHg}$, where μ_{01} and μ_i are the mean change in unmedicated DIOP from baseline at the 12-month postoperative examination for the OMNI (ab-interno transluminal viscoelastic delivery alone) and [REDACTED] respectively. Since negative μ_{01} and μ_i represent decreases in IOP, the alternative hypothesis ($H_a: \mu_{01} - \mu_i > -1.5 \text{ mmHg}$) is to prove that the mean change in unmedicated DIOP of the OMNI (ab-interno transluminal viscoelastic delivery alone) group is not worse than that of the [REDACTED] by 1.5 mmHg. In other words, the OMNI (ab-interno transluminal viscoelastic delivery alone) is not inferior to the [REDACTED] in lowering the IOP with a non-inferiority margin of 1.5 mmHg.

[REDACTED]

[REDACTED]

[REDACTED]

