10.4.1 PRIMARY EFFECTIVENESS ENDPOINT

The primary analysis of the primary effectiveness endpoint will be based on the AT population. The Baseline unmedicated DIOP will be used to impute the 12-month unmedicated DIOP for the subjects meeting any of the following criteria:

- Ocular hypotensive medications cannot be washed out properly at 12 months due to safety reasons.
- Have secondary surgical interventions (such as laser procedure or MIGS) to control IOP before the 12-month washout.
- Have any ocular procedures that can affect the IOP before the 12-month washout.

- Have IOP below 6 mmHg at 1 month or later
- Do not have the 12-month washed out DIOP due to any other reasons.

The change in unmedicated DIOP from baseline at 12 months will be calculated for each study eye as change = (12-month unmedicated DIOP – Baseline unmedicated DIOP).

The descriptive statistics (such as mean, standard deviation, median, minimum, and maximum) of the medication-free mean diurnal IOP and the change from baseline and the 95% confidence interval of the mean will be calculated for each of the three study groups. A two-sample t-test with a one-sided significance level of 0.025 will be used to compare the mean unmedicated DIOP change from baseline at 12 months for Hypotheses I and II described in Section [10.1](#). The two-sided 95% confidence interval based on the t-distribution will also be provided for the mean difference. In order to assess the pattern of the distribution, box-plots will be prepared for the medication-free mean diurnal IOP and its change from baseline for each of the three study groups.

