10.4.2 SENSITIVITY ANALYSIS

A tipping-point analysis will be performed for the primary effectiveness endpoint. Let n and m be the number of OMNI and [REDACTED] subjects that do not have the 12-month washed out DIOP due to any reasons other than the first four criteria listed in Section 10.4.1. The tipping-point analysis for Hypothesis I in Section [10.1](#) will be performed as follows:

Let X_{02} be the sample mean of the unmedicated DIOP change from baseline at 12 months for all OMNI (transluminal viscoelastic delivery AND trabeculotomy) subjects except for the n subjects and let X_i be that of the [REDACTED] excluding the m subjects. Let ω and ν be the worst and best unmedicated DIOP change from baseline at 12 months observed from the subjects. The increment of 0.05 mmHg will be used in the tipping-point analysis. The first iteration in the tipping point analysis is to use X_{02} to impute the missing values for the n subjects, use X_i to impute the missing values for the m subjects, and calculate the p-value of the statistical test described in Section [10.4.1](#). The second iteration is to use $X_{02} + 0.05$ (i.e., worse than X_{02}) to impute the missing values for the n subjects and $X_i - 0.05$ (i.e., better than X_i) to impute the missing values for the m subjects. The i th iteration is to use $X_{02} + 0.05 \times i$ to impute the missing values for the n subjects and $X_i - 0.05 \times i$ to impute the missing values for the m subjects. The iterations will stop when the p-value becomes insignificant or the imputed value for the OMNI (transluminal viscoelastic delivery AND trabeculotomy) group is worse than the ω value or the imputation for the [REDACTED] is better than the ν value, which comes first. A figure of p-value as the Y-axis and iteration as the X-axis will be provided.

The same tipping point analysis will also be performed for Hypothesis II in Section [10.1](#).

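### Scoring eyes with no 12-month washed-out DIOP for unspecified reasons as zero change can hide part of a true deficit in the non-inferiority test (Hypothesis II)

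*Combined protocol and SAP*

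**What the plan says.** Section 10.4.1 states the rule for the primary analysis: "The Baseline unmedicated DIOP will be used to impute the 12-month unmedicated DIOP for the subjects meeting any of the following criteria". Four of the five criteria describe identifiable events: washout that is unsafe, a secondary surgical intervention for IOP, another ocular procedure that can affect IOP, and low IOP from month 1. The fifth covers everything else: "Do not have the 12-month washed out DIOP due to any other reasons". Change is defined as 12-month minus baseline DIOP, so every imputed eye contributes exactly 0. The completed data go into one two-sample t-test for Hypothesis I (superiority) and Hypothesis II (non-inferiority). No separate missing-data rule is given for Hypothesis II.

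Section 8.10 gives the rationale for one group: "Subjects who have had a secondary IOP-lowering intervention will be considered treatment failures for the purpose of the endpoint analyses", and for the primary endpoint "the corresponding baseline unmedicated DIOP will be used to impute the 12-month unmedicated DIOP". It offers no such rationale for the catch-all group.

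Section 10.4.2 plans a tipping-point analysis for "subjects that do not have the 12-month washed out DIOP due to any reasons other than the first four criteria listed in Section 10.4.1". It begins from the observed arm means ("use X_i to impute the missing values for the m subjects, and calculate the p-value of the statistical test described in Section" 10.4.1) and then moves both arms against OMNI in steps of 0.05 mmHg. It also covers the second hypothesis: "The same tipping point analysis will also be performed for Hypothesis II in Section" 10.1.

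On the level of the test, Section 10.1 says "the significance level is adjusted to a two-sided significance level of 0.025 for each of the two hypotheses", which is one-sided 0.0125. Section 10.4.1 gives one-sided 0.025. Both are carried below.

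**The concern.** Baseline-value imputation is defensible for an eye that is known to have failed. The fifth criterion applies the same value to eyes not known to have failed, for example after a missed visit. In a superiority test, zeros in similar proportion in both arms pull the difference toward no effect, which is cautious. In a non-inferiority test the same pull makes a deficit look smaller. The false non-inferiority rate for Hypothesis II then depends on how many eyes miss the washed-out measurement, in which arm, and what arm difference they would have shown. None of these is controlled by the design.

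**Working it through.** **Inputs from the plan.** 459 randomized 1:1:1, so 459/3 = 153 per arm; 411 completers; about 10% drop-out (Synopsis); margin 1.5 mmHg (Section 10.1). The plan's total reproduces: 411/3 = 137, 137/0.90 = 152.2, rounded up to 153, and 3 × 153 = 459.

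**Assumed, because the planning values are blacked out.** SD of change 4 to 5 mmHg; comparator mean change -5 to -8 mmHg. Hypothesis II is read by its stated intent, OMNI viscoelastic-only not worse by 1.5 mmHg.

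**Step 1, the bias.** Let p be the missing share in both arms, D1 the arm difference among measured eyes and D2 that among missing eyes. The true difference is (1-p)D1 + pD2. The rule estimates (1-p)D1, so it loses pD2. If D1 = D2 = d, the estimate is (1-p)d, whatever the SD. For d = 1.5 it is 1.455 at 3%, 1.425 at 5% and 1.350 at 10%.

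**Step 2, type I error at a true deficit of 1.5.** With measured mean m, each arm's variance is (1-p)(SD² + m²) - ((1-p)m)², which includes the spread added by the zeros. Type I error = Φ(-z + (1.5 - expected difference)/SE).

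Example: p = 0.10, SD 4, comparator -7, OMNI -5.5.
- Comparator variance: 0.9 × (16 + 49) - 6.3² = 18.81
- OMNI variance: 0.9 × (16 + 30.25) - 4.95² = 17.12
- SE = √((18.81 + 17.12)/153) = 0.485
- Type I error = Φ(-2.241 + 0.150/0.485) = 0.027

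Over the assumed ranges:

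| Missing, each arm | Nominal 0.0125 | Nominal 0.025 |
|---|---|---|
| 3% | 0.015-0.016 | 0.030-0.031 |
| 5% | 0.017-0.019 | 0.034-0.036 |
| 10% | 0.023-0.028 | 0.044-0.051 |

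Simulating the t-test with values missing completely at random, for (mean, SD) of (-5, 5), (-7, 4) and (-8, 4), gave 0.016-0.019 at 5% and 0.024-0.026 at 10% (nominal 0.0125).

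**Step 3, does a poorer response among missing eyes remove it?** Take p = 0.10, SD 4, overall comparator mean -7, and missing eyes with half the measured response. The comparator's measured mean is then -7/0.95 = -7.37. If the arm deficit stays 1.5 in both groups, the expected difference is 1.350 and the error 0.026. If the deficit among missing eyes is halved too, the expected difference is 1.421 and the error 0.019. With equal shares, what counts is the arm difference among missing eyes, not how well they respond.

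**Step 4, unequal missingness.** If missing eyes respond like measured eyes, the bias is zero when the ratio of OMNI to comparator missing share equals the comparator mean divided by the OMNI mean. That is 5/3.5 = 1.43, 6/4.5 = 1.33, 7/5.5 = 1.27 and 8/6.5 = 1.23. Above this ratio the rule works against OMNI. Example (SD 4, comparator -7): comparator 10% and OMNI 15% give 0.85 × (-5.5) - 0.90 × (-7) = 1.625, and the error falls to 0.006 at nominal 0.0125.

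**Step 5, the planned tipping point.** I simulated the Section 10.4.2 method for the three (mean, SD) pairs, missing completely at random, nominal 0.0125. At 10% missing, the first iteration has error of about 0.022, because one value placed in every missing eye understates the variance. At a shift of about 0.55 mmHg (11 steps) it is about 0.013. At 5% missing, the first iteration gives 0.016-0.017 and a 0.5 mmHg shift 0.012-0.013.

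**The case against.** The strongest reply is that the plan already examines exactly these eyes, for exactly this hypothesis, by a method that moves against OMNI. That stands. A reader might infer that the sensitivity analysis is itself too lenient to help. The documents do not support that, because the plan shows the whole p-value curve and the variance understatement is offset after about 11 steps. What remains is narrower: Section 10.4.1, not the curve, decides the claim, and no shift is named that Hypothesis II must survive.

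Second, 10% is total planned drop-out, not the share of fifth-criterion eyes. Eyes withdrawn after a secondary intervention fall under another criterion. Eyes exited for complicated cataract extraction (Section 8.7) do not enter the As Treated population. Washout can be restarted within the visit window (Section 8.5). This also stands. At 3-5% the excess is small, and a flat statement that the error doubles would overstate the case.

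Third, the direction is not established. A reader might infer that the rule favors OMNI. Nothing in the documents suggests that missingness will differ by arm, and a modest excess in the viscoelastic-only arm reverses the bias.

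Fourth, missing eyes may have done poorly, so that zero is close to the truth. This helps less than it seems: with equal shares, the bias vanishes only if missing eyes show no arm difference (Steps 1 and 3).

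**Conclusion.** The concern holds in conditional form. With similar missing shares and the same arm deficit in missing and measured eyes, the fifth criterion shrinks a true deficit by the factor (1-p), and the type I error for Hypothesis II exceeds its nominal level: slightly at 3-5% missing, and about twofold in the upper case of 10%. The factor is exact under those conditions. The error rates rest on the assumed SD and mean change.

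This does not show that the trial will wrongly claim non-inferiority, or that the plan ignores missing data. It is a low-cost improvement to the SAP. Hypothesis I is not weakened by the rule: equal zeros shrink a true benefit, which is conservative.

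**What to change.** - Keep baseline-value imputation for criteria 1 to 4.
- For the fifth criterion, at least for Hypothesis II, use multiple imputation by arm. Fit the model only to eyes with a measured 12-month washed-out DIOP, using baseline DIOP, earlier postoperative IOP and medication use, and combine by Rubin's rules.
- Run the tipping point as shifts against OMNI from those imputations, and prespecify the shift that Hypothesis II should survive.
- Report the number of eyes under each of the five criteria by arm.
- For Hypothesis I, baseline-value imputation may stay. If multiple imputation is used there too, report both analyses.

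**Cost.** SAP wording and one additional program. The primary result for Hypothesis II would then rest on missing-at-random, which cannot be tested. In a simulation with assumed correlations, which holds for that generating model only, multiple imputation kept the error at 0.011-0.013 under missing-at-random with 5% or 10% missing (nominal 0.0125). If missing eyes were really 1 mmHg worse in OMNI and 1 mmHg better in the comparator than the model predicts, it gave 0.020-0.021 at 5% and 0.027-0.035 at 10%, against 0.026-0.029 and 0.047-0.056 for the current rule. This is why the prespecified shift matters. Hypothesis II power at no true difference and 10% missing can move either way: from 65-66% to 60-63% at (-5, SD 5), and from 76% to 83-84% at (-8, SD 4). Hypothesis II also becomes easier to pass if OMNI has clearly more ordinary missingness than the comparator.

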10.4 EFFECTIVENESS ENDPOINTS AND ANALYSIS METHODS

Descriptive statistics on continuous variables will include mean, standard deviation, median, minimum, and maximum. Confidence intervals for change from baseline will be included for selected endpoints. Categorical variables will be summarized using frequency counts and percentages. Exact confidence intervals for point estimates may be provided. Statistical testing will be one-sided with a significance level of 0.025 or two-sided significance level of 0.05 unless specify otherwise. Data listings of individual subject data may be provided.

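### The multiplicity adjustment set in Section 10.1 (two-sided 0.025 per hypothesis) is not carried into the primary tests in Section 10.4.1, which run at one-sided 0.025 with 95% intervals

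*Combined protocol and SAP*

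**What the plan says.** Section 10.1 frames the objective disjunctively: "The study goal is to determine, in reducing the IOP in eyes with OAG undergoing cataract extraction, either OMNI" with trabeculotomy is superior to the comparator, or OMNI viscoelastic delivery alone is non-inferior to it with a 1.5 mmHg margin. Because of the two hypotheses, "the significance level is adjusted to a two-sided significance level of 0.025 for each of the two hypotheses".

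Section 10.4 gives a general default: "Statistical testing will be one-sided with a significance level of 0.025 or two-sided significance level of 0.05 unless specify otherwise".

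Section 10.4.1 then names a level for the primary comparison: "A two-sample t-test with a one-sided significance level of 0.025 will be used" to compare the mean changes "for Hypotheses I and II described in Section" 10.1. It adds: "The two-sided 95% confidence interval based on the t-distribution will also be provided for the mean difference".

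Section 10.4.2 (tipping point) uses the Section 10.4.1 test and iterates until the p-value is no longer significant. It states no threshold of its own. Dunnett's test appears only in Section 10.4.4, for outcomes labelled exploratory. No visible text gives a testing order, a gatekeeping rule or a 97.5% interval for the primary contrasts.

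**The concern.** A win on either hypothesis meets the study goal, so the two tests form a family in which each gives a chance of a false claim. Section 10.1 recognises this and halves alpha. Section 10.4.1, which the programmer will follow, goes back to the unhalved level for exactly those two tests and matches it with a 95% interval.

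Two things are at stake. First, the family-wise error control stated in Section 10.1 is not delivered. Second, the plan contains two decision rules for the primary endpoint. A one-sided p of 0.02 on either hypothesis is a success by Section 10.4.1 and a failure by Section 10.1. Deciding which section governs after the data are seen would be a post hoc choice of the primary conclusion.

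**Working it through.** **Inputs**
- Level per hypothesis, Section 10.1: two-sided 0.025.
- Level per hypothesis, Section 10.4.1: one-sided 0.025.
- Allocation 1:1:1, 459 randomised, 411 completers, about 10% dropout (Synopsis; Section 8.2). This gives 411/3 = 137 completers per arm.
- Margin 1.5 mmHg (Section 10.1).
- SD and power: not readable (redacted), so any value below is an assumption.

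**1. Reproduce the plan's own figures.** The Bonferroni split is 0.05/2 = 0.025 two-sided, as Section 10.1 states. Dropout: 137/0.90 = 152.2, rounded up to 153; 153 × 3 = 459, as stated.

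**2. Put both levels on one scale.**

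| Section | One-sided level | Critical z | Matching two-sided interval |
|---|---|---|---|
| 10.1 | 0.025/2 = 0.0125 | 2.241 | 97.5% |
| 10.4.1 | 0.025 | 1.960 | 95% |

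The interval named in Section 10.4.1 matches its own test level, not the level in Section 10.1. The 97.5% interval is wider by 2.241/1.960 = 1.14, or 14%.

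**3. Family error.** Both contrasts use the same comparator arm. With equal arm sizes and variances, their correlation is (σ²/n)/(2σ²/n) = 0.5. With both nulls at their boundary,

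P(at least one false claim) = 1 − Φ₂(c, c; ρ).

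| | 10.1 level (c = 2.241) | 10.4.1 level (c = 1.960) |
|---|---|---|
| Bonferroni bound | 0.0250 | 0.0500 |
| ρ = 0 | 0.0248 | 0.0494 |
| ρ = +0.5 | 0.0232 | 0.0454 |
| ρ = −0.5 | 0.0250 | 0.0500 |

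At ρ = +0.5 the ratio is 0.0454/0.0232 = 1.95 (from unrounded values), and 0.0454 is 1.82 times the 0.025 bound implied by Section 10.1. The row for ρ = −0.5 is included because Section 10.1 prints the alternative of Hypothesis II as a difference greater than −1.5, although negative change means benefit. Tested in that printed direction, the two statistics would be negatively correlated. The printed direction needs its own correction; it does not change the conclusion here.

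**4. Does the sample size show which level was intended?** Noncentral t, 1.5 mmHg to detect (for non-inferiority, a true difference of zero against the margin):

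| Assumed SD | One-sided level | Power, n = 136 | Power, n = 137 |
|---|---|---|---|
| 4.0 | 0.0125 | 79.9% | 80.2% |
| 3.5 | 0.0125 | 89.9% | 90.1% |
| 4.4 | 0.025 | 79.99% | 80.3% |

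In each row 137 is the smallest n that reaches 80% or 90%. The sample size therefore fits the Section 10.1 level under round SD values, but it also fits the Section 10.4.1 level. It does not decide the question.

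**The case against.** Several points on the other side are fair.

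- **Section 10.4 alone is not in conflict.** It is a default that yields to more specific text, and it names neither a hypothesis nor an interval level. This stands. The conflict is between Sections 10.1 and 10.4.1. The default cannot rescue the plan, though, because Section 10.4.1 does specify a level for these two tests, and it is the unadjusted one.
- **The slip could be in either place.** The number 0.025 appears in both sections and only the sidedness differs. Section 10.1 might have meant a one-sided family rate of 0.05 split into two halves. The documents do not rule that out. But that family rate would be twice what Section 10.1 now states, and each test would sit at the plan's ordinary default, so the adjustment would have no visible effect. The text would need correcting on that reading too.
- **The sample-size match proves nothing.** Correct, as step 4 shows. The finding does not rely on it.
- **The error figures rest on assumptions.** They take equal variances, equal arms and both nulls at the boundary, while the primary population is As Treated, where arm sizes may differ. This stands, but the ratio is close to two for every correlation examined.
- **Redacted lines follow the hypotheses in Section 10.1.** They may hold the SD and power. They cannot make two explicit, different levels for the same tests agree.

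**Conclusion.** The concern holds, and the plan must be corrected. Sections 10.1 and 10.4.1 set incompatible levels for the same two primary hypotheses, and the one in the analysis section is unadjusted. Following Section 10.4.1 gives a family error of 4.5% instead of 2.3% under the shared-comparator calculation (5.0% instead of 2.5% at the Bonferroni bound), so it nearly doubles. The existence of the conflict rests on no assumption. Its size rests on equal arms, equal variances and both nulls at their boundary. Which section the sponsor meant to govern cannot be read from the documents, but Section 10.1 is the only place that gives a reason for its level.

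**What to change.** - **Section 10.4.1:** test each of Hypotheses I and II at one-sided 0.0125 (two-sided 0.025), and replace the 95% interval for the two primary mean differences by a two-sided 97.5% interval.
- **Section 10.4.2:** state 0.0125 as the one-sided threshold at which the tipping-point iterations stop.
- **Section 10.4:** say that the default level does not apply to the primary hypotheses.

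**Optional.** Holm's procedure keeps the same family error bound: test the smaller p-value at one-sided 0.0125 and, if significant, the other at one-sided 0.025. With both true effects at 1.5 mmHg from their null boundary, an assumed SD of 4.0, 137 per arm and correlation 0.5 (2 million simulated draws), power per hypothesis rises from 80.6% to 85.1%, and power for both from 69.5% to 78.5%. If Holm is chosen, the intervals must be defined to match. Otherwise a hypothesis could be declared at 0.025 while its 97.5% interval still crosses the margin or zero. The fixed split avoids this and is sufficient.

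**Cost.** No new data or subjects, only SAP text finalised before unblinding. The possible price is power. If the redacted calculation used one-sided 0.0125, nothing is lost. If it used one-sided 0.025, for example with SD 4.4, power per hypothesis at 137 per arm falls from 80.3% to 71.5%. The sponsor should check the unredacted assumptions and state the level used.

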8.7 SURGICAL PROCEDURE

Only eyes with uneventful cataract extraction will receive one of the following surgical procedures based on randomization:

1. Ab-interno transluminal viscoelastic delivery (up to 360 degrees) and trabeculotomy (at least 180 degrees and up to 360 degrees) using the OMNI Surgical System
2. Ab-interno transluminal viscoelastic delivery (up to 360 degrees) using the OMNI Surgical System
3. [REDACTED]

Eyes with complications related to previous glaucoma interventions or cataract extraction (such as posterior capsular rent or vitreous presentation) should be exited from the study. The region where the trabeculotomy procedure is performed (e.g. superior hemisphere) and the extent of trabeculotomy should be recorded on the case report forms.

[REDACTED]

[REDACTED]

Surgeons should follow their standard intra-operative and peri-operative medication regimen.

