10.2.2 INTENT TO TREAT (ITT) AND AS TREATED (AT) POPULATIONS

The Intent to Treat (ITT) analysis population will include all subjects randomized and grouped according to randomization assignment (as randomized) regardless if the assigned procedure is performed. The As Treated (AT) population will consist of the subjects that undergo the assigned procedure and will be grouped according to actual treatments. For this study, the AT population will be used for the primary analyses of

the primary and other effectiveness endpoints. The effectiveness analyses may be performed for the ITT population if needed.

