10.3 DEMOGRAPHICS AND BASELINE CHARACTERISTICS

Subject demographics (age, race/ethnicity and gender) will be summarized by study group for the ITT, AT, and Safety populations using descriptive statistics. Age will be summarized as a continuous variable and categorized into the four groups based on the observed quartiles.

The baseline medicated IOP and washout (unmedicated) IOP will be summarized by study groups for the ITT and AT populations. They will be treated as continuous variables. The number of glaucoma medications in use at enrollment will be prepared for each of the study groups using descriptive statistics for categorical variables.

Medical and Ocular history will be summarized for each study group by number and percentage of subjects in the ITT and AT population.

For the Safety Population, ITT, and AT populations, subject accountability will be prepared based on Table G.1 of ANSI Z80.27-2014.

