10.4.3 COVARIATE ANALYSIS

The following variables will be examined for their prognostic value to the primary effectiveness endpoint using the AT population with the imputation used for the primary analyses:

- Age group (based on observed quartiles)
- Gender (male and female)
- Race/ethnicity
- Baseline unmedicated DIOP group (based on observed quartiles)
- Number of ocular hypotensive medications at screening
- Study Site

For the primary effectiveness endpoint, two-way ANOVA with study group (three groups), one of the factors listed above, and the interaction between the study group and the factor will be used to check the possible covariate effects. A p-value of 0.15 will be used for evaluating the possible covariate effects. It should be noted that the subgroups of these covariates will be re-examined and may be re-categorized or eliminated due to small sample size (if there are < 10 subjects within each subgroup).

The scatter plots of the 12-month unmedicated DIOP versus the baseline unmedicated DIOP along with a 45° line will be provided. The scatter plot of the percent change in unmedicated DIOP from baseline to 12 months versus the baseline unmedicated DIOP will also be provided. The Box plots of the change and percent change in unmedicated DIOP from baseline to 12 months will be prepared for each category of the covariates (except for the study site).

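### Baseline DIOP enters the primary t-test only by subtraction; a prespecified baseline-adjusted ANCOVA would be a nearly free, probably small, improvement

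*Combined protocol and SAP*

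**What the plan says.** Section 10.4.1 builds the endpoint by subtraction ("The change in unmedicated DIOP from baseline at 12 months will be calculated for each study eye as change") and then applies an unadjusted test to both hypotheses: "A two-sample t-test with a one-sided significance level of 0.025 will be used to compare the mean unmedicated DIOP change". The tipping-point analysis in 10.4.2 uses the same test at each iteration ("calculate the p-value of the statistical test described in Section").

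Baseline DIOP appears elsewhere only descriptively or as a screen:

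- Section 10.3: "The baseline medicated IOP and washout (unmedicated) IOP will be summarized by study groups for the ITT and AT populations".
- Section 10.4.3 plots outcome against baseline ("The scatter plots of the 12-month unmedicated DIOP versus the baseline unmedicated DIOP along with" a 45-degree line). It also puts baseline quartiles, and separately site, into two-way ANOVAs with interaction: "A p-value of 0.15 will be used for evaluating the possible covariate effects".

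Randomisation is stratified by site only (8.6). Site is not in the primary test. On the population, 10.2.2 says "the AT population will be used for the primary analyses of" the effectiveness endpoints, and 8.7 says "Only eyes with uneventful cataract extraction will receive one of the following surgical procedures based on randomization"; eyes with complicated extraction leave the study.

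**The concern.** Subtracting baseline is fully efficient only if the 12-month value rises one for one with baseline. If the slope is below 1, eyes that start higher fall further whatever the treatment. An arm that starts higher by chance then shows a larger mean fall. If that is the viscoelastic-only OMNI arm, the imbalance helps the non-inferiority claim of Hypothesis II; if that arm starts lower, it hurts. (Direction here follows the verbal definition of non-inferiority in 10.1.) The effect averages out over hypothetical repeats, but not in the one trial that is run.

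The plan would reveal the problem without an agreed response. Section 10.3 would show an imbalance and the 10.4.3 plot would show a slope below 1, yet no adjusted contrast or interval is prespecified. An adjustment chosen after seeing the data is open to dispute. The As Treated population adds to this, since exits after randomisation can also unbalance the arms. ANCOVA would correct only the part carried by measured baseline DIOP.

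**Working it through.** **The plan's own figure.** 411 completers / 3 = 137 per arm; 137 / 0.9 = 152.2, rounded up to 153; 3 x 153 = 459, which matches. The derivation of 411 is not visible.

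**Inputs from the documents.** 153 randomised and 137 completing per arm; margin 1.5 mmHg (10.1); one-sided 0.025 (10.4.1); baseline eligibility 24-39 mmHg (synopsis); baseline value carried to 12 months for failures and missing data (10.4.1), so those eyes have change 0.

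**Assumed inputs.** Baseline SD sb = 2.7 (also 2.0, and 15/sqrt(12) = 4.33 for a uniform spread over 24-39); residual SD se = 3.5; mean change m = -10 mmHg and slope b, both in non-imputed eyes; imputed share p = 48/459 = 10.5%, where 48 = 459 - 411.

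**Variance reduction.** With k = (1-b)² sb², the variance of change is (1-p)(k + se² + p m²), of which baseline explains (1-p)² k. The fraction removed is g = (1-p)k / (k + se² + p m²). For b = 0.4 and sb = 2.7: k = 0.36 x 7.29 = 2.62, so g = 0.895 x 2.62 / (2.62 + 12.25 + 10.46) = 9.3%.

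| Setting | b = 0.4 | 0.6 | 0.8 | 1.0 |
|---|---|---|---|---|
| sb 2.0 | 5.3% | 2.5% | 0.6% | 0% |
| sb 2.7 | 9.3% | 4.4% | 1.1% | 0% |
| sb 4.33 | 20.5% | 10.4% | 2.9% | 0% |
| sb 2.7, p = 0.20 | 6.0% | 2.8% | 0.7% | 0% |

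With m from -6 to -10 and se from 3.0 to 4.5 (sb 2.7), the ranges are 7.1-15.3%, 3.3-7.5% and 0.8-2.0% at b = 0.4, 0.6 and 0.8. If the effect is proportional (an assumption), a 20% fall means b = 0.8, and a fall from 24 to 18 mmHg means b = 0.75 (g = 1.8%).

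**Effect of one imbalance.** A two-sided 1-in-20 imbalance is 1.96 x 2.7 x sqrt(2/153) = 0.61 mmHg (0.64 at 137 per arm). The shift in the unadjusted estimate is (1-p)(1-b) x imbalance. The t-test's standard error is SE = sqrt(2(1-p)(k + se² + p m²)/153). Given that imbalance, the false non-inferiority rate at the margin is 1 - Φ((1.96 SE ∓ shift) / (SE sqrt(1-g))).

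| | b = 0.4 | 0.6 | 0.8 | 1.0 |
|---|---|---|---|---|
| SE (mmHg) | 0.545 | 0.529 | 0.519 | 0.516 |
| Shift (mmHg) | 0.33 | 0.22 | 0.11 | 0 |
| Share of margin | 22% | 14% | 7% | 0% |
| Rate, imbalance favours OMNI | 7.6% | 5.6% | 3.9% | 2.5% |
| Rate, opposite imbalance | 0.4% | 0.8% | 1.5% | 2.5% |

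The average over randomisations remains 2.5%.

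**Simulation of the proposed model.** Three arms of 153; baseline truncated to 24-39 (SD 2.61); viscoelastic-only arm at the 1.5 mmHg boundary; p = 0.105, 0.20, or 0.10/0.20/0.10 by arm; b from 0.2 to 1.0; 4,000 runs per setting.

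- At p = 0.105, variance fell by 8-9%, 4%, 1% and 0% at b = 0.4, 0.6, 0.8 and 1.0.
- ANCOVA with HC3 errors had coverage 94.4-95.8% and one-sided type I error 1.7-2.9% (t-test 1.9-3.0%; Monte Carlo error about 0.25 points).
- A common-variance ANCOVA reached 3.3%, hence the robust errors.
- In the 5% of runs where the viscoelastic-only arm started furthest above control (p = 0.105), the t-test's mean error was -0.34, -0.20 and -0.14 mmHg at b = 0.4, 0.6 and 0.8, against -0.02, +0.02 and -0.02 for ANCOVA.

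**A second simulation** (137 per arm, mean change -8, residual SD 3.5, b 0.3-0.8) gave reductions of 1-28% with no imputation and about 0-17% with 15-30% imputed.

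**The case against.** The strongest reply is that both analyses are valid and the expected gain is trivial. At slopes 0.75-0.8 the base case is worth about 2 eyes in 137 per arm (137 x 1.1-1.8%) and about 0.01 mmHg of interval half-width. The 7.6% rate needs both a slope of 0.4 and a 1-in-40 imbalance in one direction; at slope 0.8 the same imbalance gives 3.9%. Any unadjusted test behaves this way when a covariate is prognostic. This stands, and it limits the point to an improvement.

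The conditional rates also depend on which alpha applies. Section 10.1 sets two-sided 0.025 per hypothesis (one-sided 0.0125), while 10.4.1 uses one-sided 0.025. At the 10.1 level the rates are about 4.2%, 3.1% and 2.0% at slopes 0.4, 0.6 and 0.8, against a nominal 1.25%. The pattern is unchanged.

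An adjusted comparison could be extracted from the quartile model in 10.4.3. But that model is there to test prognostic value, its categories may be redrawn or dropped, and no treatment contrast or interval is promised from it.

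Finally, the tipping-point values in 10.4.2 are arm-mean changes unrelated to baseline, so under ANCOVA the starting iteration is not exactly neutral given baseline. That is true, but minor.

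**Conclusion.** The point holds as a recommended improvement. The primary t-test is valid, with correct average coverage. The likely precision gain is about 1-4%, rising to about 9% at slope 0.4 and 20% only with a wide baseline spread as well. The better reason to adjust is protection in the single trial run: a 1-in-20 baseline imbalance could move the Hypothesis II estimate by 0.11-0.33 mmHg at slopes 0.8 to 0.4, or 7-22% of the margin. At slope 1 there is nothing to gain.

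Every SD, the slope, the mean change and the imputed share are assumptions, so the size cannot be confirmed from the visible documents. The 10.5% covers planned drop-out only; 10.4.1 imputes for four further reasons, so the share may be higher and the gain smaller. With few imputed eyes and a low slope the gain could be larger. As Treated numbers per arm are not given; 153 is the randomised figure.

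**What to change.** In 10.4.1, prespecify an ANCOVA of 12-month change on treatment (three arms) with continuous baseline unmedicated DIOP as covariate, in the same population and with the same imputation rule. Use HC2 or HC3 standard errors to allow unequal arm variances. Take both primary contrasts and their intervals from this model, at the alpha level obtained once 10.1 and 10.4.1 are reconciled. In 10.4.2, keep the imputed values and take each p-value from this model. Retain the t-test as a sensitivity analysis. Adding site, as a random effect or with small sites pooled by a rule fixed in advance, is optional; no separate precision gain from it was shown.

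The cost is SAP wording and one regression model, using about one degree of freedom and no new data. In the first simulation the worst case, at slope 1, was an interval 0.4% wider with HC3 and 0.0% wider with HC2. The change should be made before 12-month results by arm are seen.
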